Musically-Guided Paced Breathing Improves Mental Health in War-Affected Adolescents

Study Protocol and Statistical Analysis Plan

NCI Number: NCT06988800

January 21, 2024

Participants

Students were included in this study if they were children aged 13-17 years and enrolled at a school in a war-torn area in the West Bank in the Middle East. Students were excluded if they had a known diagnosis that may have impeded their participation (e.g., epilepsy, substance abuse, attention-deficit/hyperactivity disorder). In order to have 90% power to detect a medium effect size ($f = .25$), 130 participants would be required, and the total number enrolled was 213. Consent forms stated that the goal of the intervention was to reduce anxiety and manage stress. The study protocol was approved by an Institutional Review Board that consisted of two independent researchers in the study region.

Procedure

Participants were randomly assigned, stratified by age and gender, to an intervention or control condition. After all consents were collected, an individual external to the study team divided participants into near equal groups based on age and gender, which were then used to assign participants to one of the three conditions. Only the individual who randomized the participants and the group facilitators were provided access to the document linking the name and de-identified participant identifier.

Participants in the control condition completed other typical after-school activities while participants in the intervention condition completed one of two breathing interventions: paced breathing (paced), or mindful breathing (mindfulness). Participants in the control condition were given the opportunity to complete the intervention after the study ended. All participants in the intervention and control conditions completed a pre-intervention measure of anxiety, depression, and self-efficacy. Participants in the intervention condition then completed 12 sessions of the guided paced breathing audiovisual intervention, held 2 times a week for 5 weeks. After the 4th

week of the intervention, all participants in both the intervention and control conditions completed a mid-intervention measure of anxiety, depression, and self-efficacy. The study was then paused for one month during Ramadan, and resumed at the beginning of the following month. After the 5th total week of the intervention, all participants in both the intervention and control conditions completed a post-intervention measure of anxiety, depression, and self-efficacy.

Guided Paced Breathing Audiovisual Intervention

Each intervention session was conducted by the school teacher, who guided groups of approximately ten participants in classrooms. The groups were separated by gender and age (e.g., 16-year-old boys). Participants were seated comfortably with a clear view of a screen displaying the audiovisual intervention, and the audio was played at a comfortable volume. Each session began with an educational introduction, which outlined the benefits of paced breathing, such as how it can positively impact well-being and mental health (e.g., "A strong sense of well-being helps you to feel good about yourself and the way your life is going, which can have a hugely positive impact on your mental health").

Following the introduction, the intervention transitioned into a three-minute audiovisual guided paced breathing exercise. The paced breathing condition used timed auditory and visual cues to guide participants through breathing cycles at a rate of five breaths per minute, designed to stimulate the parasympathetic nervous system and promote relaxation. The audiovisual cues included spoken instructions, music, and breath-like sounds. The tonal audio cues rose in pitch during inhalation and fell during exhalation, creating a clear auditory signal for breath pacing. The same harmonic drone used in the mindfulness intervention provided a calming background, though here it was combined with the rhythmic pacing. Visually, the pacing was synchronized

with the image of a lotus flower opening during inhalation and closing during exhalation, reinforcing the breathing rhythm.

Mindfulness Intervention

The mindfulness intervention employed a similar visual setting, featuring the same lotus flower graphic. However, instead of rhythmic pacing, the lotus flower remained open at the start of the session and gradually closed over the course of the 3 minute exercise. This visual served as a symbolic anchor for the participant's growing awareness and focus.

The audio component of the mindfulness intervention featured a female narrator guiding participants through mindfulness exercises, focusing on breath awareness and cultivating non-judgmental attention to thoughts and feelings. Ambient tonal sounds, including a harmonic drone with slow timbral changes, played softly in the background to support relaxation. Importantly, no rhythmic audio cues were included to avoid inducing breathing entrainment. This setup emphasized passive, mindful observation rather than active breath control, encouraging participants to observe their bodily sensations and thoughts without judgment.

Measures

Demographics. Participant age and gender were collected from families as part of the student's involvement in the after-school program.

Revised Children's Manifest Anxiety Scale (RCMAS). To measure the level and nature of anxiety symptoms, the RCMAS Arabic version was administered to participants via a web-based survey. The RCMAS is a self-report questionnaire that lists feelings or actions and was administered to all participants pre- and post-intervention. Participants answer "yes" if that item is generally descriptive of their own feelings or actions, or "no" if not. The RCMAS produces a total anxiety score based on 28 items, with three subscales: physiological anxiety,

worry/oversensitivity, and social concerns/concentration. Higher scores represent more anxiety symptoms. Both the English and Arabic versions of the RCMAS have been shown to have acceptable reliability and validity in school-aged children. Similar to previous studies using the RCMAS, if at least 80% of items for each scale was present, missing data was imputed using the within-subject mean of the non-missing items in the same scale. In the current sample, the total score showed good internal consistency ($\alpha = .82$).

The Self-Efficacy Questionnaire for Children (SEQ-C).

The Self-Efficacy Questionnaire for Children (SEQ-C) measures three types of self-efficacy: (1) social self-efficacy, measuring children's capability to deal with social challenges; (2) academic self-efficacy, measuring children's perceived capability to master academic affairs; and (3) self-regulatory efficacy, measuring children's ability to resist peer pressure to engage in high risk activities.

Translated PHQ-9

A validated measure of depressive symptoms, consisting of nine items assessing the frequency of depressive symptoms over the past two weeks. The PHQ-9 has demonstrated strong psychometric properties, including reliability and validity in clinical and non-clinical populations, including the translated Arabic version.

Data Analysis

Analyses were conducted using R. Group differences at baseline in anxiety, depression, and self-efficacy scores were examined using ANCOVAs and post hoc Tukey pairwise tests. For the primary analyses, four analyses of covariance (ANCOVAs) were conducted. For each ANCOVA, the independent variables were condition (paced breathing or mindfulness intervention vs. control) and time of observation (before or after the intervention), the dependent

variable was the behavioral scale (RCMAS, SEQ-C, PHQ-9) at post-intervention, and the covariate was gender. Exploratory general linear models (GLMs) were conducted to examine whether gender moderated the relationship between condition and anxiety or depression symptoms. For significant GLMs, post-hoc GLMs were conducted to examine the relationship between condition and anxiety or depression symptoms within each subgroup. All tests were two-tailed, no test assumptions were violated, and findings were considered significant at $p < .05$.

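### Assignment is stratified by age and gender but the primary ANCOVAs adjust for gender only; under individual assignment this costs a little precision, and under other readings the direction is not assured

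*Combined protocol and SAP*

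**What the plan says.** **Assignment.** The Procedure section states: "Participants were randomly assigned, stratified by age and gender, to an intervention or control condition". It adds that someone independent of the trial "divided participants into near equal groups based on age and gender, which were then used to assign participants to one of the three conditions". No age categories, block size or allocation ratio are given. The Participants section limits entry to "children aged 13-17 years and enrolled at a school", so at most five single years of age are possible.

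**Availability of age.** Under Measures (Demographics): "Participant age and gender were collected from families as part of the student's involvement in the after-school program".

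**Analysis.** The Data Analysis section says that the dependent "variable was the behavioral scale (RCMAS, SEQ-C, PHQ-9) at post-intervention, and the covariate was gender". It also lists "time of observation (before or after the intervention") as an independent variable beside condition. Age does not appear in that section, and its absence is not explained. No subject term is named.

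**Delivery.** The section on the paced breathing intervention describes sessions run in classrooms for about ten students at a time, each group of one gender and one age.

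**The concern.** Stratified assignment balances age across the arms, so age adds almost nothing to the true sampling variance of the condition effect. A model without age does not know this. It leaves the age variance in the residual and computes its standard error as if age could still be imbalanced. The estimate is unbiased, but the interval is a little wide and the test runs a little below its nominal 5%. The usual remedy is to analyse by the factors used for assignment, and here one of the two is dropped without comment.

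At stake is a small amount of precision in each of the four primary analyses. Validity is at stake only if assignment was not made to individuals within strata.

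**Working it through.** **Inputs from the document:** N = 213 enrolled; 130 required for 90% power at f = .25; three conditions; two-sided 5% level; ages 13 to 17; two genders.

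**Assumptions (not in the document):**
- Age explains a share R² of the outcome variance left after gender: 0, .02, .05 or .10.
- Strata are single year of age by gender, so 5 × 2 = 10 cells.
- The three arms are near equal within each cell.

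**Step 1. The plan's own figure.** The 130 is reproduced by a repeated-measures between-groups F test with two groups, two measurements and correlation .5 (power .904 at N = 130). The document states none of these three settings. A three-group ANCOVA at f = .25 needs 207. With 213 its power is 91.1%, which is the baseline used below. With equal arms and both active arms shifted equally from control, f = .25 means a shift of .25/√(2/9) = .53 SD.

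**Step 2. Individual assignment, post-intervention scores, one row per participant, no clustering.**
- Standard error ratio, reported to true: 1/√(1 − R²). This gives 1/√.98 = 1.010, 1/√.95 = 1.026 and 1/√.90 = 1.054.
- Large-sample type I error of the 2-df condition test: .05 raised to the power 1/(1 − R²). This gives 4.7, 4.3 and 3.6%. For a single two-sided contrast, 2[1 − Φ(1.96/√(1 − R²))] gives 4.8, 4.4 and 3.9%.
- Simulation of the 2-df test (40,000 trials per setting) agrees:

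| Assumed R² | SE too large by | Type I error, gender only | Type I error, with age | Power at f = .25, gender only | Power at f = .25, with age |
|---|---|---|---|---|---|
| 0 | 0.0% | 5.0% | 5.0% | 91.1% | 91.0% |
| .02 | 1.0% | 4.7% | 5.0% | 91.2% | 91.6% |
| .05 | 2.6% | 4.3% | 4.9% | 91.7% | 92.6% |
| .10 | 5.5% | 3.7% | 5.1% | 92.0% | 93.9% |

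Repeat simulations gave gender-only type I error of 4.7–4.8, 4.3–4.4 and 3.5–3.7% at R² of .02, .05 and .10. Power lost is 0.4, 0.9 and 1.9 points. R² = .10 is not a ceiling: at R² = .20, a contrast with 90% power after age adjustment has 85.3% without it, a loss of 4.7 points.

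**Step 3. Within-subject change** (pre-post correlation .5 and an equal age effect at both times assumed). Age cancels: the standard error ratio is 1.000 at every R², type I error is 5.0–5.1% and power 91.0–91.2%, with or without age.

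**Step 4. Whole groups assigned** (about 20 single-age, single-gender groups of about ten, assumed). The gender-only 2-df test has type I error of about 9, 14 and 25% at R² of .02, .05 and .10. For one contrast, the reported standard error is 0.80 of the true one at R² = .05 and 0.70 at .10. Adding age brings these ratios to 1.00 and 0.985.

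**Step 5. Classroom clustering** in the active arms, individual assignment, R² = .05. The gender-only ratio is about 1.00 at an assumed intraclass correlation of .01 or .02, and 0.955 at .05. With age added the ratios are 0.977, 0.977 and 0.929.

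**Step 6. Pre and post rows stacked with no subject term** (correlation .5 assumed). Type I error of the condition main effect is 12.9, 12.0 and 9.9% without age at R² of .02, .05 and .10, and 13.6, 13.6 and 12.6% with age.

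**The case against.** The strongest reply is that this is a choice about precision and not an error. The document nowhere says that age predicts any of the scales. Over a five-year age range the share explained may be close to zero, and then nothing is lost. Even at R² = .10 the analysis in step 2 stays valid and loses about 2 points of power. This stands, and it is why the point is minor. It does not explain why one stratification factor was kept and the other dropped.

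A second reply is that the direction depends on facts the document leaves open. This also stands. The Procedure wording favours individual assignment but does not exclude assigning whole groups (step 4). Clustering can cancel or reverse the conservatism (step 5). The listed time factor permits a change analysis (step 3) or stacked rows (step 6). The size of any gain also rests on age categories that are not stated.

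A reader might infer that leaving age out biases the condition effect or inflates false positives. Under individual assignment within strata it does neither. A reader might equally infer that the omission is always harmless, or that the reported standard error is too large overall. The document does not support that either: step 2 isolates the effect of omitting age and is not the net error once clustering and the form of the model are counted.

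**Conclusion.** The mismatch is a fact: two stratification factors, one adjusted for, the other collected but unused and unexplained. If individuals were assigned within strata, post-intervention scores are compared with one row per participant, and clustering is set aside, the standard error is about 1.0, 2.6 and 5.4% too large at assumed R² of .02, .05 and .10. Type I error is about 4.8, 4.4 and 3.6%, and about 0.4 to 2 points of power are lost at f = .25. A larger R² would cost more. The effect is nil if age is not prognostic or if within-subject change is tested. Outside those conditions the direction is not assured, and with whole-group assignment and a prognostic age the gender-only test over-rejects. Minor; a free improvement. Confidence is medium, because neither the strength of age nor the contrast tested is stated.

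**What to change.** 1. State the age categories used for stratification and whether individuals or whole groups were assigned.
2. Settle the model before adding a covariate: one post-intervention row per participant, or a model with a subject term. Do not add age to stacked pre and post rows without a subject term, where it slightly worsens the over-rejection (step 6).
3. Add age, in its stratification categories, beside gender in each primary ANCOVA. The document is written in the past tense and already reports data, so show the age-adjusted result next to the gender-only result and label it as added later. If age is to stay out, give the reason.

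**Cost under individual assignment:** no new data and at most four degrees of freedom, if single years were the categories. Residual degrees of freedom go from 209 to 205 and the 5% critical F from 3.039 to 3.040. If age explains nothing, power at f = .25 goes from 91.07% to 91.06%. If whole groups were assigned, the adjusted standard error is larger (in the simulation at R² = .05, 0.191 against 0.161 under individual assignment), because that is the honest precision of such a design.

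Adding age does not deal with classroom clustering or repeated measures. Both need their own treatment, and step 5 shows that age adjustment removes whatever margin the omission had been lending.

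### No planned analysis names the mid-intervention scores, so the single post estimate, taken after a one-month pause and one further week, cannot tell no effect from one that faded

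*Combined protocol and SAP*

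**What the plan says.** The Procedure sets out three measurement occasions for every arm: before the programme, after week 4, and after week 5. At the second, all participants "completed a mid-intervention measure of anxiety, depression, and self-efficacy". Then: "The study was then paused for one month during Ramadan, and resumed at the beginning of the following month". The last occasion is described so: "After the 5th total week of the intervention, all participants in both the intervention and control conditions completed a post-intervention measure".

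The Data Analysis section lists condition and "time of observation (before or after the intervention" as the independent variables, the scale at the post visit as the dependent variable, and gender as the covariate. The mid visit is not mentioned there. No reason is given for collecting it or for leaving it out, and nothing says how the pause is to be handled.

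Two entries under Measures bear on this. The RCMAS paragraph says the scale "was administered to all participants pre- and post-intervention", with no mid administration. The PHQ-9 is described as "nine items assessing the frequency of depressive symptoms over the past two weeks".

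**The concern.** The mid visit is the only post-baseline visit that follows an unbroken block of sessions. The post visit combines three things: whatever the first four weeks did, how far that lasted through a month in which the study was paused, and what one more week added. The plan reports this as one before-or-after comparison and offers nothing that separates the parts.

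If the post contrast is null, the reader cannot tell whether the breathing programmes did nothing or had an effect that wore off. If it is positive, the reader cannot tell a lasting effect from one that arose in the last week. The visit that could answer this is described as completed by all participants. Leaving it out without explanation also invites the question whether it was looked at and set aside.

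**Working it through.** **The plan's own figure.** The Participants section gives 130 for 90% power at f = 0.25. With a noncentral F test at two-sided 0.05, k groups, t time points and correlation ρ between them (ρ = 0.5 assumed; not in the documents), the noncentrality is λ = f²·N·t / (1 + (t − 1)ρ).
- For k = 2 and t = 2 at N = 130: λ = 0.0625 × 130 × 2 / 1.5 = 10.83, power 0.904. The smallest N is 129, or 130 with equal groups, so the figure reproduces.
- With three time points the answer would be 116 (two groups) or 141 (three groups).

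The stated figure thus fits a before-and-after analysis without a mid visit. This agrees with the Data Analysis text but does not decide the point.

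**Timeline.** Mid is at 4 weeks. Post is at 4 + about 4 + 1 = about 9 weeks. That no sessions were held in the pause is inferred from the word paused, which is a fair reading. The session count is not consistent: the Procedure gives 12 sessions, but twice weekly for five weeks is 2 × 5 = 10. At two a week, 8 come before mid, leaving 2 or 4 after the pause depending on which total is meant. Those figures must be reconciled.

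**PHQ-9 recall.** If the post measure was taken d days after a seven-day final week, 14 − 7 − d of the 14 recall days fall in the pause: 7 if d = 0, none if d = 7. The documents do not give d.

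**Do mid scores sharpen the post contrast?** Let r be the mid–post correlation given baseline and q the fraction of post scores missing. The variance using mid scores, relative to complete cases, is [(1 − r²)/(1 − q) + r²](1 − q) = 1 − q·r². With q = 0 this is 1: no gain. The Procedure says all participants completed the post measure and reports no missing visits. (The RCMAS imputation rule concerns missing items, not missing visits.)

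**What baseline adjustment gives.** Assume equal variance at each visit and correlation ρ between baseline and post.
- Against post scores alone without baseline, the ratio is 1 − ρ²: 0.91, 0.75, 0.51 at ρ = 0.3, 0.5, 0.7.
- If the two-level time factor is instead read as a comparison of change scores, their variance is 2(1 − ρ) = 1.4, 1.0, 0.6, and the ratio is (1 − ρ²)/[2(1 − ρ)] = 0.65, 0.75, 0.85.

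The text does not settle which is meant: with a post-only dependent variable, a before-or-after factor cannot vary.

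**The mid/post average.** Given baseline, its variance relative to post alone is (1 + r)/2.
- For assumed r = 0.5, 0.6, 0.7: 0.75, 0.80, 0.85.
- If all three visits are equally correlated at ρ, then r = ρ/(1 + ρ). For ρ = 0.3, 0.5, 0.7 this is 0.23, 0.33, 0.41, and the ratios are 0.62, 0.67, 0.71.

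This is a different estimand. If an effect of size δ at mid had vanished by post, the average would be δ/2.

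**The case against.** The strongest reply is that the end of the programme is a legitimate primary time point, the pause applied to all arms, and adding a mid contrast is a preference. The first two parts stand: the randomised comparison is not biased by the pause, and post should remain primary. The third does not. The plan gives the reader one number that covers a four-week effect, its persistence and a further week, when a measurement that would separate them is described as taken.

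A reader might infer several stronger claims that the documents do not support.
- **That the mid scores were discarded.** The exploratory models state no time point, and four ANCOVAs are announced for three named scales. Use of the mid scores is unstated rather than excluded.
- **That participants with a mid but no post score are lost.** The Procedure says all participants completed the post measure. Any missing fraction would be invented.
- **That using mid scores is worth extra sample size for the main question.** The variance reduction belongs to the mid/post average. It is a power gain only if the effect is similar at both visits, which is the very thing in doubt.
- **That a mid score exists for every outcome.** For anxiety the RCMAS paragraph and the Procedure disagree.

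It is also fair to say that the document is written in the past tense, reports an internal consistency in the current sample and states that no assumptions were violated. Pre-specification may no longer be possible.

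**Conclusion.** The point holds as one of interpretation and incomplete use of collected data, not of bias. Three findings rest on the text alone: no analysis names the mid scores; the only post-baseline visit named follows a one-month pause and one week; and the documents conflict on the RCMAS schedule.

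The sizes rest on assumed correlations. For the primary post contrast, the mid scores contribute essentially nothing when post scores are complete. Adding baseline as a covariate reduces variance by 9% to 49% against an unadjusted post comparison, or by 15% to 35% against change scores, for ρ from 0.3 to 0.7. The reduction of 15% to 38% for the mid/post average applies to that secondary quantity only. The share of the PHQ-9 window lying in the pause is at most about half and cannot be fixed from the documents.

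The sponsor should act on this: the change is cheap and uses only data the Procedure describes as already collected.

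**What to change.** 1. Reconcile the RCMAS paragraph with the Procedure on whether anxiety was measured at mid, and state what use, if any, was made of the mid scores.
2. For each outcome with mid scores, fit one repeated-measures model to mid and post with three-level condition, visit, condition × visit, baseline score, baseline × visit, gender and age, and an unstructured within-participant covariance. Age belongs there because randomisation was stratified by it.
3. Where no mid score exists, fit an ANCOVA on the post score adjusted for baseline, gender and age.
4. Keep post as the primary contrast, and describe it as the effect after a one-month pause plus one further week.
5. Report the mid contrast as secondary. The mid/post average is optional and should be presented as a different estimand. If outcomes have already been seen, label both post hoc.

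Cost: plan wording and analysis code, with no new data. The price is more comparisons. Each added time summary brings two contrasts against control, so reporting both mid and average adds 2 × 2 = 4 per outcome, or 12 over three scales (8 if the RCMAS has no mid score). None should carry a confirmatory claim.

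### Breathing sessions ran in teacher-led groups of about ten, but the models have no group term; if scores stay correlated within groups, standard errors for post-intervention condition tests are too small

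*Combined protocol and SAP*

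**What the plan says.** All places are in the combined protocol and SAP.

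- **Delivery** (Guided Paced Breathing Audiovisual Intervention): "Each intervention session was conducted by the school teacher, who guided groups of approximately ten participants in classrooms". On composition: "The groups were separated by gender and age (e.g., 16-year-old boys").
- **Which arms were grouped.** The statement stands under the paced-breathing heading. The Mindfulness Intervention section does not describe grouping. For that arm it is an inference, from the words on each intervention session and from the Procedure section, which uses one intervention name for everyone in the intervention condition: "Participants in the intervention condition then completed 12 sessions of the guided paced breathing audiovisual intervention, held 2 times a week for 5 weeks". Whether controls were grouped is not stated.
- **Assignment** (Procedure): "Participants were randomly assigned, stratified by age and gender, to an intervention or control condition". The next sentence is less clear about the unit. An external individual "divided participants into near equal groups based on age and gender, which were then used to assign participants to one of the three conditions".
- **Analysis** (Data Analysis): the primary ANCOVAs have condition and time of observation as factors, the scale score at post-intervention as outcome, and gender as the only covariate. The exploratory models add moderation by gender. No section gives a session-group or teacher term, a random effect, a cluster-robust variance or an ICC. The section also states that test assumptions were met.

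**The concern.** Adolescents who attend the same sessions share peers, a room and a leader. If that makes their later scores more alike than those of adolescents in different groups, a breathing arm of 71 carries less information than 71 independent observations. An ANCOVA on individuals does not see this. It reports standard errors that are too small, p-values that are too low and intervals that are too narrow for the condition tests.

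Independence of observations is one of the assumptions that the Data Analysis section says were met, yet nothing shows that it was examined despite group delivery. At stake are results that fall just under .05, because the reader has no ICC with which to judge them.

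**Working it through.** **Inputs from the documents.** 213 enrolled, required N of 130, f = .25, 90% power (Participants); three conditions (Procedure); groups of about ten, separated by gender and age (Guided Paced Breathing section); ages 13-17 (Participants); two-sided .05 (Data Analysis).

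**Assumptions.** Equal arms, 213/3 = 71. ICC .01/.05/.10, since none is given. Two layouts per arm: 5 ages x 2 genders = 10 groups of 71/10 = 7.1, or 7 groups of about 10. Controls ungrouped unless stated. Outcome is the post-intervention score, adjusted for gender.

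**1. The plan's own figure.** The 130 is reproduced by a between-subject repeated-measures test with 2 groups, 2 measurements and correlation .5 (all undisclosed): noncentrality .0625 x 130 x 2/1.5 = 10.8, power .904. That calculation contains no allowance for groups. If every arm were grouped in tens, 130 x 1.09/1.45/1.90 = 142/189/247 at the three ICCs.

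**2. Design effect**, DE = 1 + (m - 1) x ICC, and **standard-error ratio** (true over reported). A grouped arm mean has variance DE/71 and an ungrouped one 1/71, while the ANCOVA assumes 1/71 for each. The ratio is sqrt((DE + 1)/2) for one breathing arm against an ungrouped control, and sqrt(DE) if both sides are grouped.

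| | ICC .01 | .05 | .10 |
|---|---|---|---|
| DE, m = 7.1 | 1.06 | 1.31 | 1.61 |
| SE ratio, ungrouped control | 1.02 | 1.07 | 1.14 |
| SE ratio, both sides grouped | 1.03 | 1.14 | 1.27 |
| DE, m = 10 | 1.09 | 1.45 | 1.90 |
| SE ratio, ungrouped control | 1.02 | 1.11 | 1.20 |
| SE ratio, both sides grouped | 1.04 | 1.20 | 1.38 |

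**3. Rejection rate implied by the ratio.** With 213 - 4 = 209 residual degrees of freedom the critical value is 1.971. The chance that |t(209)| exceeds 1.971 divided by the ratio, with an ungrouped control, is .0535/.0678/.0859 (m = 7.1) and .0552/.0764/.1032 (m = 10).

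**4. Simulation under no effect** (40,000 trials per setting, ordinary least squares on condition and gender). Rejection at nominal 5%, ICC .01/.05/.10:

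| Test | 10 groups of about 7 | 7 groups of about 10 |
|---|---|---|
| One breathing arm vs ungrouped control | 5.4/6.9/8.7% | 5.6/7.7/10.7% |
| One breathing arm vs grouped control | 5.9/8.7/12.3% | 6.1/10.5/16.1% |
| Three-arm test, only paced grouped | 5.2/6.6/8.4% | 5.6/7.5/10.3% |

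The three-arm test with both breathing arms grouped and controls ungrouped rejects in about 5-6/8-10/12-16% across the two layouts and repeated simulations. All tests are near 5% at ICC 0. If only paced breathing was grouped, mindfulness against control stays near 5%.

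**5. Offset from omitting age.** If individuals were randomised within age-gender strata, age is balanced across arms. It then adds nothing to the true variance of the condition difference, but it stays in the residual variance because it is not a covariate, and so makes the reported standard error too large. With age explaining an assumed 5-10% of variance (10 groups, ungrouped control), one breathing arm against control rejects in about 4.4-5.1% at ICC .01 and 5.8-6.5% at ICC .05. At ICC .10 the rate remains about 8%.

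**The case against.** **The ICC may be close to zero.** The content was standardised: after the introduction, "the intervention transitioned into a three-minute audiovisual guided paced breathing exercise". No group discussion is described, and the RCMAS was a self-report web survey. This stands. It limits the likely size, but a teacher still conducted each session, and without a reported ICC nobody can confirm it.

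**Individual stratified randomisation makes grouping harmless.** This is partly right. Likeness due only to shared age or gender does not inflate error, and step 5 shows that it slightly lowers it. Randomisation cannot remove correlation that arises afterwards in shared sessions.

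**The post-only model may not be the one used.** This stands. Time is listed as a factor, and the 130 fits a repeated-measures calculation. In a stacked pre/post model with no participant term (assumed pre-post correlation .5), even at ICC 0 the condition-by-time test rejects in only about 0.2-0.3% and the condition main effect in about 13.6-13.8%. That is a different defect, from ignored repeated measures.

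**Stronger readings that the documents do not support.** A reader might infer that the reported tests have a true error of 10-16%. That needs an ICC of .10 with groups of about ten (or grouped controls), and none of this is documented. A reader might also infer that this is a cluster-randomised trial. One Procedure sentence says participants were assigned, the next could mean whole age-gender groups, and the text does not settle it.

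**Conclusion.** The point holds in conditional form. Group delivery is documented for paced breathing and reasonably inferred for mindfulness, and the models leave it out. Under a post-only model, any positive within-group correlation that remains after gender, and after age under individual stratified randomisation, makes the standard errors for condition tests too small unless the age offset cancels it. The assumptions statement is unsupported for independence.

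With ungrouped controls the effect on the named comparison with control is small at ICC .01 and moderate at .10. Under individual randomisation the age offset can bring it to about nominal at ICC .01. It is larger if controls were grouped or if whole age-gender groups were allocated. In the latter case the baseline comparisons are affected too; under individual randomisation they are not. If the ICC is near 0, conclusions do not change.

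The rates rest on the assumed ICCs, equal arms of 71, groups that stayed the same across sessions, and the two layouts. The omission is clear from the text, its size is not, and it should be fixed.

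**What to change.** 1. State the unit of assignment, and which arms used session groups that stayed fixed.
2. Analyse post-intervention scores with a random intercept for session group, using Kenward-Roger or Satterthwaite degrees of freedom. The model is partially nested, with each control as their own cluster, or nested in all arms if controls were grouped or whole groups were allocated. Under individual stratified randomisation, add age as a covariate. If time stays in the model, add a participant random effect, and limit the group effect to post-baseline scores only if individuals, not whole groups, were allocated.
3. Report the ICC with its interval, and confine the assumptions sentence to what was checked.
4. If session membership was not recorded, use the arm-by-age-by-gender cell as a proxy group, since age and gender were collected (Measures, Demographics). Also show results with standard errors inflated for ICC .01/.05/.10 by the ratios in step 2, with group-based degrees of freedom.

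**Cost.** One mixed model in R, and recovery of membership or use of the proxy. The Procedure section says who held the identifier link ("Only the individual who randomized the participants and the group facilitators were provided access to the document linking the name and de-identified participant identifier") but not that membership was recorded. Intervals widen somewhat. For one breathing arm against an ungrouped control at ICC 0, Satterthwaite degrees of freedom are about 4/(1/17 + 1/69) = 55 with 10 groups per arm, or 4/(1/11 + 1/69) = 38 with 7. Here 17 and 11 are the between-group degrees of freedom pooled over the two breathing arms, before any age term. The ratio of t quantiles to t(209) is then about 1.02-1.03, which is 2-3% wider.
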